## **9.5 Routine Adverse Event Reporting**

All Adverse Events **must** be reported in routine study data submissions. **AEs reported expeditiously through CTEP-AERS must also be reported in routine study data submissions (Section [12.4](#)).**

Adverse event data collection and reporting, which are required as part of every clinical trial, are done to ensure the safety of patients enrolled in the studies as well as those who

will enroll in future studies using similar agents. AEs are reported in a routine manner at scheduled times during the trial using Medidata Rave. For this trial the Adverse Event CRF is used for routine AE reporting in Rave.

## 9.6 Correlative Studies

### 9.6.1 Pharmacokinetic Assessment (All Surgical Patients): Exploratory

This correlative study is mandatory for all patients in the surgical arm. It is also optional for patients on the medical arm who progress while on treatment and undergo a clinically indicated resection while on study drugs.

Blood, cerebrospinal fluid, and tissue samples will be collected on the day of surgery at time points specified in Section [9.2](#). Details for the collection, processing, storage, and shipment of samples are provided in the **Laboratory Manual**.

We hypothesize tumor drug concentration will directly correlate with functional ERK inhibition, and may correlate with extent and duration of response in individual patients. Levels of total (protein-bound and unbound) encorafenib and binimetinib, as well as the active metabolite of each parent compound, will be measured as continuous variables using validated LC/MS methods in order to calculate the tumor-to-plasma ratio as an estimate of tumor permeability. (51) We will compare drug concentrations between enhancing and non-enhancing brain, and CSF. This assay will be performed by the ABTC-associated Applied Pharmacology Core at Johns Hopkins led by [name].

### 9.6.2 Resistance Mechanisms (All Patients): Exploratory

There are two parts to this correlative study. Archival tumor tissue for genomic analysis will be obtained from all patients in the study (medical and surgical cohorts) as outlined in Section [9.1](#).

In the second component, FFPE post-treatment surgical tissue will be obtained from all patients in the surgical cohort (as described in the **Laboratory Manual**), and from patients who progress while on treatment and undergo an additional surgery. These slides will be obtained using the same procedure as described for archival tumor tissue.

A significant proportion of patients with melanoma or glioma treated with BRAF/MEK inhibitors develop therapeutic resistance over time as defined by relative insensitivity to targeted therapy leading to progressive disease. Thus, determination of resistance mechanisms is critical for future drug development. Putative mechanisms of resistance are defined as genomic or expression level changes that are likely to confer resistance, either because they have already been defined as such in other cancers, or because they are predicted to have a protein-level effect decreasing sensitivity to BRAF/MEK inhibitors. There are many known examples in other tumor types including mutations in *BRAF*, *RAS*, overexpression of *COT*, *BRAF*, *CRAF*, or *YAP1*, activation of receptor tyrosine kinases, or loss of *NF1*, *PTEN*, or *STAG2/3*.

Whole exome sequencing (WES) and RNA sequencing (RNAseq) will be performed to compare mutations in pre- and post-treatment samples (Illumina HiSeq 2500). WES & RNAseq will also be performed on unpaired baseline specimens from patients on the medical arm who do not respond to treatment with the assumption that a *de novo* mechanism of resistance exists in these tumors. We will use whole blood for comparison to filter out germline SNPs in all patients. Germline mutations will not be identified or reported. Results will have variant calling through standard procedures associated with the Computational Biology Core at Johns Hopkins. We will manually examine remaining variants to exclude sequencing errors and ensure sufficient coverage depth of at least 20x. We will compare candidate mutations against published genomic alterations conferring resistance, such as second-site mutations in *BRAF*, RAS mutations, and loss of *PTEN* and/or *NF1*. (20-23) For RNAseq results, we will use pathway analysis of the differentially expressed genes to identify potential alterations responsible for acquired resistance within individual patients and across the entire cohort. This assay will be performed by the laboratory of Drs. [name] and [name] at Johns Hopkins.

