## Surgical Arm Treatment Schema

Subjects in the surgical cohort must be candidates for a clinically-indicated surgery and must have a BRAF V600E/K-mutated high-grade glioma or a low-grade glioma with high clinical suspicion for progression to high-grade. These subjects will take encorafenib and binimetinib in combination at their FDA-approved doses (see Section 4.3 for administration details) for 10-14 days prior to surgery, with a preference for 14 days, though a minimum of 10 days is acceptable. The last dose of both drugs will be administered two hours prior to surgery. Specimens will be collected as described in Section 9.6 and processed as described in the **Laboratory Manual**.

After surgery, the subjects will not take further encorafenib or binimetinib until a study visit to assess their neurological exam, physical exam (or telemedicine physical evaluation), and performance status, at 2-6 weeks post-operatively. At time of restarting combination treatment, subjects will follow the schedule listed above for the medical cohort, and will continue treatment as defined in Section 10.1.

Patients with histopathology inconsistent with high-grade glioma (either treatment effect or low grade glioma) will be replaced. Overall survival will be assessed from the first day that patient receives drug to death from any cause.

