#### 9.6.6 Archival Tumor Tissue: Exploratory

Archived tumor tissue from the most tumor recent resection demonstrating active tumor will be collected from all patients, when sufficient tissue is available. If sufficient tissue is not available from the most recent surgery, then tissue from an earlier surgery is acceptable, if available, including from the initial resection at diagnosis.

At the time of registration, prior to beginning treatment, a tumor tissue form indicating availability must be completed and signed by a pathologist for each study participant. This form provides written documentation of the availability of tissue for this study and the pathologist's agreement to send it as described below.

20 unstained slides, preferentially from the most recent tumor resection, will be requested. The associated pathology report from the institution of collection should be shipped with the slides.

Details for the collection and shipment of tissue samples are provided in the **Laboratory Manual**.

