#### **11.4 Analysis of Exploratory Endpoints:**

1. Clinical outcomes such as tumor response rate, progression-free survival, and overall survival for cohort 3 (recurrent BRAF-V600 mutated high-grade primary brain tumors not included in the cohort 1 and cohort 2). The standard definitions of these outcomes will be used as described above. The outcomes will be summarized and presented descriptively.
2. Encorafenib and binimetinib concentrations in enhancing brain tissue and cerebrospinal fluid (surgical cohort): descriptive summary on mean and standard deviation of drug will be reported. Additional analyses are summarized in Section [9.6.1](#).
3. Putative mechanisms of drug resistance are defined as identified genomic or functional alterations in post-treatment tissue that are not present, or are present in a much smaller variant allele frequency (VAF), in pre-treatment tissue, and that could contribute to decreased drug sensitivity. Candidate mutations will be measured using the methods described in Section [9.6.2](#). These results will be manually curated and confirmed against known gene lists.
4. Functional inhibition of the ERK signaling pathway: the functional inhibition of the ERK signaling pathway is defined by the measurements of phospho-ERK and RSK protein, quantitated relative to total ERK. Due to the exploratory nature, the pathway changes after drug exposure will be reported using descriptive summary.

5. BRAF-V600 DNA mutant fraction: the mutant fraction is measured as the number of BRAF V600E or –K transcripts relative to BRAF wild-type transcripts, corrected for differences in sequencing efficiency and the quantity of starting material. The mutant fraction in CSF and plasma will be collected over multiple time points during the study. The fraction change overtime will be presented as a liner or non-linear trend after data checking. Descriptive summary at each individual time point and multiple time points will be presented graphically.

A more detailed description of exploratory correlatives are provided in Section [9.6](#).

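### The pre/post rule for calling a resistance mutation is stated on variant allele frequency with no tumour-content adjustment, so a purity difference between paired samples can mimic or mask clonal change

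*Combined protocol and SAP*

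**What the plan says.** Section 9.6.2 plans the comparison: "Whole exome sequencing (WES) and RNA sequencing (RNAseq) will be performed to compare mutations in pre- and post-treatment samples". It does not mention VAF. The operative rule is in Section 11.4 item 3, which defines putative mechanisms as post-treatment alterations "that are not present, or are present in a much smaller variant allele frequency (VAF), in pre-treatment tissue". The same item requires that the alteration could plausibly lower drug sensitivity, and that results be curated by hand against known gene lists. The VAF difference has no numeric threshold.

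On laboratory method, Section 9.6.2 says: "Results will have variant calling through standard procedures associated with the Computational Biology Core at Johns Hopkins". It adds a manual check to "ensure sufficient coverage depth of at least 20x", and on germline variants: "We will use whole blood for comparison to filter out germline SNPs in all patients".

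On tissue, Section 9.6.6 prefers the most recent resection showing active tumour. If that yields too little, "tissue from an earlier surgery is acceptable, if available, including from the initial resection at diagnosis". Post-treatment tissue comes from the surgical cohort, operated on while on drug, and from patients who have further surgery at progression. Section 9.6.5 requires frozen-section confirmation of glioma before the extra research specimens are taken. For the surgical arm, Section 4.1 adds: "Patients with histopathology inconsistent with high-grade glioma (either treatment effect or low grade glioma) will be replaced".

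No supplied section gives a minimum tumour percentage, a purity estimate, a copy-number adjustment or a cancer-cell fraction for the tissue comparison.

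**The concern.** VAF is the mutant share of all DNA read at a locus, so normal cells in the sample dilute it. The two samples in a pair come from different operations, one before and one after drug exposure, and nothing in the plan makes their tumour content alike. The tissue checks establish that tumour is present, not how much. The blood comparison removes germline variants but does not correct for normal cells in the tumour sample.

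A change in VAF can therefore arise with no change in the tumour's clones, and a real clonal change can be cancelled. Exploratory objective 3 rests on this contrast, and there will be few pairs: six planned surgical patients (Section 11.2) plus those who have surgery at progression. One misclassified pair could alter the description noticeably.

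**Working it through.** The plan states no sample size, power or error rate for this analysis, so there is no figure to reproduce. What can be checked is how the rule behaves.

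**Inputs.** From the documents: the VAF rule (11.4 item 3) and the 20x depth floor (9.6.2). Assumed, because the documents are silent: purities of 10% to 80%, a heterozygous mutation in a diploid region, and two illustrative calling rules (at least 1, or at least 3, variant reads).

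**Formula.** With purity p, cancer-cell fraction CCF, m mutant copies per mutated cell and tumour copy number CN:

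VAF = p × CCF × m / [p × CN + 2(1 − p)]

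For m = 1 and CN = 2 this is p × CCF / 2. The observed fold change is then (purity ratio) × (CCF ratio).

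**1. False enrichment (CCF = 1 in both samples)**

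| Purity before → after | VAF before → after | Apparent change |
|---|---|---|
| 30% → 60% | 0.15 → 0.30 | 2-fold |
| 20% → 80% | 0.10 → 0.40 | 4-fold |
| 10% → 70% | 0.05 → 0.35 | 7-fold |

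**2. Hidden expansion (CCF truly 0.2 → 0.8)**
- Purity 80% → 20%: 0.2 × 0.8 / 2 = 0.08 and 0.8 × 0.2 / 2 = 0.08. No change is seen.
- Purity 60% → 30%: 0.2 × 0.6 / 2 = 0.06 and 0.8 × 0.3 / 2 = 0.12. A 4-fold expansion reads as 2-fold.

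**3. The absence limb at 20x.** For a clonal mutation, P(zero variant reads) = (1 − p/2)^20.

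| Purity | P(0 reads) | P(fewer than 3 reads) |
|---|---|---|
| 10% | 36% | 92% |
| 20% | 12% | 68% |
| 30% | 4% | 40% |
| 50% | 0.3% | 9% |
| 80% | about 0% | 0.4% |

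For purity 20% then 80%, the chance of absent before and present after under the 3-read rule is 0.677 × 0.996 = 67% at 20x, and 0.2% at 100x. More depth cures this limb. It does not change the 4-fold ratio in step 1.

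**4. Does adjustment work?** In the diploid case CCF = 2 × VAF / p. Step 1 at 20% and 80%: 2 × 0.10 / 0.2 = 1.0 and 2 × 0.40 / 0.8 = 1.0. Step 2 at 80% and 20%: 2 × 0.08 / 0.8 = 0.2 and 2 × 0.08 / 0.2 = 0.8. Both are right in expectation.

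**5. Is dividing by the same-sample BRAF V600 VAF enough?** Not as the main method. If BRAF and the candidate both have VAF 0.10 and depth 20, BRAF shows zero reads 12% of the time (ratio undefined), and the ratio is at least 2-fold off its true value of 1.0 a further 52% of the time. At 50x and 100x that second figure is 34% and 15%. The ratio also ignores copy number at the candidate locus. With one copy lost there (CN = 1, m = 1) and purity 80%, VAF is 0.8 / (0.8 + 0.4) = 0.67 against 0.40 for BRAF, so the ratio reads 1.67 with CCF still 1.0.

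**The case against.** The best defence has four parts.

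- **Silence is not a statement.** A reader might infer that the plan prescribes an unadjusted comparison. It does not say so. The variant-calling procedures are not spelled out, and the Laboratory Manual is not supplied; either could contain a purity step. This stands. The gap is that the rule is written on VAF and no adjustment is stated.
- **Other filters apply.** A reader might infer that any unchanged clonal mutation in a tumour-poor archival block would be called. That is too broad. The alteration must plausibly reduce sensitivity and survive manual curation against gene lists. This confines false enrichment to plausible resistance genes, such as a pre-existing alteration of PTEN or NF1. It does not restore an expansion that the VAF rule has excluded. Section 9.6.2 does define putative mechanisms by likely effect, without a VAF contrast, so a known resistance mutation with flat VAF could still be reported under that wording. The two definitions disagree and need reconciling.
- **The tissue rules are tighter than they may look.** Archival tissue is not any earlier block at will; an earlier one is a fallback. Surgical-arm patients whose histology shows treatment effect or low-grade tumour are replaced. That removes the extreme specimens, but not high-grade tumour mixed with treatment effect, and it is stated only for the surgical arm.
- **The consequence is small.** The analysis is exploratory and descriptive, and Section 11.2 says no trial decision rests on the surgical cohort. This stands.

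**Conclusion.** The concern holds as a minor point about an exploratory analysis. As written, the rule in 11.4 item 3 cannot separate a change in clones from a change in tumour content, and it can err in both directions. The size depends wholly on purities that the documents do not give: 2-fold to 7-fold false enrichment over the assumed range, and complete masking only when the fall in purity exactly offsets the expansion. The 12% chance of zero reads uses the plan's own 20x floor but an assumed purity of 20%; at 50% purity it is 0.3%.

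The point is limited to paired DNA comparisons. It does not extend to the RNAseq expression analysis or to the unpaired baseline samples from non-responders, which have no pre/post VAF contrast. Nor do the documents support reading it as a threat to the response, survival or safety analyses.

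**What to change.** In Section 11.4 item 3, cross-referenced from 9.6.2, and for paired DNA comparisons only:

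1. Apply the lower-before-treatment limb to cancer-cell fraction estimated from the same exome data, adjusted for purity and for copy number at the candidate locus. State how large a difference counts.
2. Use the same-sample BRAF V600E/K VAF as a check, where depth is adequate and BRAF is clonal with stable copy number. Every patient has this mutation by inclusion criterion 2. It should not be the main denominator, because BRAF is itself a candidate resistance locus and the ratio is noisy in tumour-poor samples.
3. Call a mutation absent before treatment only where depth and purity give a prespecified detection probability; otherwise record it as not assessable.
4. Report the raw VAFs, depth and estimated purity for both samples beside the adjusted values.
5. Reconcile the definitions of a putative mechanism in 9.6.2 and 11.4. If the sequencing core already adjusts for purity, a sentence saying so and naming the method would meet most of this.

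The cost is some copy-number and purity modelling on data already generated; no new samples or assays are needed. Estimates will be imprecise at low purity or low depth, and some pairs will become not assessable.

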### 9.6.3 Pharmacodynamic studies (All Surgical Patients): Exploratory

This correlative study is mandatory for all patients in the surgical arm. It is also optional for patients on the medical arm who progress while on treatment and undergo a clinically indicated resection while on study drugs.

Blood and tissue samples will be collected on the day of surgery at time points specified in Section [9.2.1](#). Details for the collection, processing, storage, and shipment of samples are provided in the **Laboratory Manual**.

Functional inhibition of ERK signaling will be measured by relative expression levels of phospho-ERK and p90 Ribosomal S6K (RSK) as quantified on immunoblot using standard procedures for quantification in the software ImageJ (<https://imagej.nih.gov/ij/index.html>). The ratios of phospho-ERK to total ERK and RSK to total ERK will be quantified as continuous variables. ERK inhibition will be measured as the fold-change in functional ERK activity (pERK/tERK and RSK/tERK, separately) between baseline (derived from archival tissue) and the surgical specimen. Functional inhibition will be correlated with peak serum concentrations separately for pERK and RSK to determine whether there is any correlation. This assay will be performed by the laboratory of Drs. [name] and [name] at Johns Hopkins.

### 9.6.4 Circulating Tumor DNA (All Patients): Exploratory

This correlative study is mandatory for all patients, but there are two stages.

All patients on the medical and surgical arms will have a blood specimen (20 mL whole blood per time point) collected at pre-specified time points (see below). The blood samples will be collected, processed, stored, and shipped as described in the **Laboratory Manual**.

Cerebrospinal fluid donation is optional (other than the CSF collected during surgery for surgical arm patients, which is required) and requires additional, specific consent on consent form from patients on the medical and surgical arms. In patients who consent, it should be collected at the pre-specified time points below, same as for blood. It can be collected via Ommaya reservoir or lumbar puncture at the discretion of the treating physician (6 mL per time point). A patient does not need to consent to all these time points, but may elect to donate CSF for only one of these time points. Cerebrospinal fluid will be collected, processed, stored, and shipped as described in the **Laboratory Manual**.

Time Points:

- Baseline
- Pre-Cycle 3
- Pre-Cycle 7
- Off Treatment

Tumor-specific circulating DNA distinguishes from normal DNA by the occurrence of point mutations in tumor derived DNA. Tumor-specific circulating DNA can be detected in CSF as well as blood. (46) We will use Safe-SeqS, a next-generation sequencing assay that enables the detection of tumor specific DNA in a high background of normal DNA with high sensitivity and specificity. (52) In this study, the BRAF V600E or K mutation is used to identify and monitor the fraction of tumor DNA. Tumor-specific circulating DNA as measured by the Safe-SeqS assay will be a continuous variable and shall be represented as a ratio between the mutant and wild-type allele evaluated (mutant fraction). The development of techniques to analyze genetic alterations in blood and CSF of patients is a rapidly changing field. The methods used to adequately detect mutated DNA and to differentiate it from wild type DNA will be adjusted and modified as appropriate on an ongoing basis. This assay will be performed by the laboratory of [name] at Johns Hopkins.

### 9.6.5 Overview of Biospecimen Collection on Surgical Arm

Patients with a history of BRAF-V600E/K mutated glioma who are planning to undergo surgical tumor resection and are eligible to participate in this study (based on inclusion/exclusion criteria in Sections [3.2](#) and [3.3](#)) may participate in the surgical arm. Patients on the medical arm who experience likely progression and require a clinically indicated surgery are also eligible if they continue drug until the day of surgery. All patients in this cohort should take their last dose of binimetinib and encorafenib two hours prior to surgery. At the time of this clinically indicated surgery, biospecimens will be collected, after the induction of general anesthesia, in the following order:

- 1) Prior to tumor manipulation: Whole blood (total of 40 mL) and cerebrospinal fluid (6 mL).
  - a. Blood will typically be obtained from an arterial line and/or venous line placed as part of standard of care, placed immediately on wet ice, and processed as described in the **Laboratory Manual**.

- b. CSF will be obtained in one of three ways per discretion of the neurosurgeon ± principal investigator, placed immediately on wet ice, and processed as described in the **Laboratory Manual**. Determination as to the method of CSF extraction (specifically, whether or not a lumbar puncture is indicated) will be determined prior to surgery and patient will confirm on consent form.
    - i. By Ommaya reservoir access prior to the surgical procedure.
    - ii. By lumbar puncture after the induction of anesthesia so as to induce no additional discomfort to the patient.
    - iii. During surgery, from cisternal aspiration, if the cistern were to be opened as part of the planned surgical procedure.
    - iv. During surgery, from ventricular aspiration, if the ventricle were to be encountered as part of the planned surgical procedure.
- 2) At tumor manipulation: Enhancing and non-enhancing brain tumor tissue.
- a. After frozen section confirmation of glioma and confirmation with the pathologist that sufficient material has been obtained for clinical diagnostic processing (grading, sub classification, and the relevant genetic testing), additional tumor specimens will be obtained for this study and processed as described in the **Laboratory Manual**.
  - b. The specimen locations will be determined by the neurosurgeon based on MRI and tissue appearance with one intended to be in enhancing and the other in non-enhancing brain per MRI-contrast pre-operative image. The sample location will be noted with MRI wand and correlated with pre-operative MRI scan.
- 3) At closure: Whole blood (10 mL), obtained as above.
- 4) After tissue is processed: 20 unstained FFPE slides from current resection.

20 unstained slides from the repeat resection should be requested and processed as outlined in the **Laboratory Manual** and shipped, along with a copy of the associated pathology report.

